The benefit expected from the product's effectiveness on refractory chronic neuropathic pain with a pain relief in these patients who are beyond all other types of pain treatments.

Ketamine at a dose of 1 mg / kg is well tolerated in clinic and in various studies around ketamine. The contraindications of ketamine are allergy, severe hypertension, severe heart failure: patients excluded from our study. In the conditions of the study, dosage and duration of infusion, the risk of adverse effect is minimal.

The most common side effects are: drowsiness, euphoria, hallucinations, tinnitus, nightmares and disorientation, nystagmus (rhythmic oscillation of the eyes), arterial hypertension and tachycardia. Patients being scoped and monitored medically in post interventionnal oversight room, the slightest side effect will be detected and treated.

In our study the administration will be intravenously, it will be a single infusion of ketamine at a dose of 1 mg/kg, over a period of two hours. As mentioned previously, it appears that the effectiveness of the product in clinical studies appears to doses higher than 0, 5 mg/kg administered slowly on over an hour (29). Where our choice of infusion is over 2 hours. We have chosen a single infusion to avoid the effects of the repeated infusion over several days which showed liver adverse effects in the recent literature with doses regimens of ketamine very important. (36)

The clinical trial will be conducted in accordance with the Protocol presented in this document following compliance with good clinical practices.

Description of the study population: spinal cord injury patients with chronic pain with or without bedsore (ulcer pressure)

The incidence of spinal cord injury (SCI) is about 20 / million residents in France, more than 1,200 new cases per year, and prevalence is more than 250 / million residents, or about 20,000 patients in France. For SCI patients, the prevalence of chronic pain is 65-85%, of which 40% are neuropathic and one-third are severe. Neuropathic pain are the hardest to relieve and there is a strong correlation between their presence and a difficult becoming both psychological, physical and social. Pain affects sleep, quality of life, interpersonal, socio-professional rehabilitation or return to work. His prognosis is not good with a low long term

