For hospitalized patients, their usual follow-up will be resumed after the release of recovery. Inclusion in the study lasts 7 days in total, with a follow-up by phone and by a tracking notebook, the last phone call held at 7 days of infusion.

Description of study stop, rules or criteria of exclusion for subjects.

All serious adverse events, defined by: ketamine or its excipients, shock, pushed hypersensitivity reaction hypertensive greater than 180/110 defined as hypertensive emergency according to the HAS, a depression respiratory causing a desaturation < 92% in air, a marked psychodysleptique reaction causing a major stir, that can be linked to the administration of the product will immediately stop the infusion, supported by a doctor specializing in Anaesthesia-resuscitation and the statement from pharmacovigilance and the ANSM.

Each observation will include a reporting of serious adverse events card.

The patient will be analysed in the study for intention to treat analysis, the last pain expressed will be chosen as main analysis on which the study will be judged.

Per-protocol analysis will also take place, excluding patients who have not benefited from the full dose of ketamine.

Any withdrawal of consent before the infusion will result in the exclusion of the subject of the study.

Withdrawal of consent after the end of the infusion, will lead to the choice of the subject, an analysis by intention to treat if the patient accepts the conservation of already saved data or also if it wishes the ouster of the subject of the study so that the deletion of all the data related to the patient, in agreement with the notion of free consent informed, revocable at any time.

The study will end permanently after the 48th patient tracking.

Is 7 days after the inclusion and treatment of the 48th patient (see calculation of the number of subjects needed here below)

Safety assessment and management of serious events

The investigator has the responsibility to report every adverse events.

Definitions

Adverse event : any harmful event occurring in a person who lends itself to biomedical research, that this event is related to research or the product on which this research is defined as adverse event

Side effect: all adverse event due to research.

We class them in subclasses:

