-Serious expected adverse effect: already mentioned in the summary of the characteristics of the product for drugs with permission of placing on the market as is the case in our study. This definition also applies to the test drug when administered to a population off-label of the AMM.

-Unexpected serious adverse: if its nature, severity or evolution differ from those described in the most recent version of the brochure for investigators or the summary of the characteristics of the drug.

Serious adverse event : any event or adverse reaction which results in death, is endangering the life of the person who lends itself to research, requires hospitalization or prolongation of hospitalization, causes an inability or a significant or long-lasting, handicap or well translates an anomaly or a congenital defect.

The expression "which endangers the life of the person" is reserved for an immediate existential threat, at the time of the adverse event regardless of the consequences of a corrective or palliative therapy.

Deaths, whatever their cause, including when they correspond to a progression of the disease being treated, are considered serious events.

Other events do not meet the above qualifications, may be considered to be "potentially serious", including certain biological abnormalities. The medical judgment of the investigator

or the sponsor may lead to the declaration of such events in the same way that the events "serious."

All new interesting research (or the product used) and may adversely affect the safety of the people who lend themselves to research will be of appropriate urgent safety and information without delay by the promoter from the competent authority and the patients committee protection.

Serious adverse event reporting:

The investigator has the obligation to report within 24 hours to the promoter all serious adverse events occurred in all patients included in the study:

- during the active study,
- in the weeks after the discontinuation of treatment
- within the established time of follow-up of tolerance without treatment, before (phase out wash or withdrawal) or after the active phase.
- After the trial, regardless of the deadline, as no other cause than the research cannot reasonably be offending,

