A temporary stoppage of the study will be considered when new fact (as defined above) in order to give himself time to reassess the balance of benefits and risks of research jointly with ANSM .

Ratings criteria

Main evaluation criterion

Decrease (more than 30%) the intensity of neuropathic pain evaluated at the moment on a numeric scale of 10 points between H0 and H4.

Secondary evaluation criteria

Score of NPSI on H0, J1, J4, J7 Under the NPSI score; H0, J1, J4, J7 Score of depression HADS or Hamilton J0, J7 Pain timeline between J0 and J7. Painful surface evaluated on mapping H0, J1, J4, J7 Decrease in scores between baseline and H4. Side effects of the drugs evaluated H0 and H4 of the end of the infusion then in J1. Auto assessment of relief of pain and mood improvement at 7 days after infusion. Blood assays pre administration of Ketamine then H4 after end of Directors of: serotonin (5-HT), kynurenine (KYN), indoleamine 2, 3-dioxygenase 1 (IDO1) activity (ratio KYN/TRP), kynurenic acid (KA) and quinolinic acid (QA), as well as 3 proinflammatoires cytokines it- 1β , IL-6, and TNF - α

Patient selection, exclusion and data collected.

The criteria for inclusion:

- SCI with central neuropathic pain with or without bed sores.
- Adults speaking and understanding the French
- With chronic neuropathic pain, according to the IASP definition
- Painful intensity > or = 6 / 10 during the week prior to the inclusion
- Spinal cord injury a few either the origin (traumatic, degenerative, tumor, post operative), responsible for paraplegia in a chronic state.
- Able to give their informed consent after a clear, fair and appropriate information
- Having given their agreement by a written consent signature.

No inclusion criteria:

- Patients with a hypersensitivity to ketamine or one of its excipients.
- Another Interventional trial participation, or participation in another trial interrupted for less than 3 months.

- Patient unable to give their consent
- Pregnancy or lactation underway
- Refusal of consent signature
- Cardiovascular diseases particularly associated with rhythm disorders and severe heart failure, coronary, discovered by examination, ECG or biological assessment or known.
- HTA unstabilized > 180/100 mmHg
- Severe hepato cellular and / or renal failure.
- For the group without sores, lack of ongoing inflammatory pathology noted by the interrogation (fever, sepsis, urinary tract infection)

Exclusion criteria:

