As defined above, any adverse product will lead to the immediate cessation of the infusion however the patient will be analysed in the study for an intention to treat analysis. If it refuses the analysis or withdraws consent at any time of the study patients will be excluded from the study in accordance with best practices.

After the duration of 7 days of participation and follow-up, the patient will be released the study as planned in the Protocol (end of final follow-up).

Data collected on patients:

These data will include: full name, Date of birth, the patient's Age, height, weight, BMI, sex, usual treatments, Presence of allergy, medical conditions, age of evolution of chronic pain, spinal cord injury, the more important pain in the week prior to the inclusion. Score NPSI, HADS Score, painful Surface evaluated on mapping, Patient having already benefited from infusion of ketamine before, history of use of other non-drug therapies for treatment of chronic pain.

The data collected during the study will be for 7 days with the periods already mentioned: Score of NPSI on H0, J1, J4, J7, NPSI underscore; H0, J1, J4, J7, Score of depression HADS J0, J7 (for all elements in H1 and H4 previous evaluation by the clinician investigator, J1 J4 J7 by a self-report filled at home or by telephone call) Painful surface evaluated on H0, J1, J4, J7 (H1 and H4 by the clinician investigator, J1 J4 J7 by the patient at home on a sheet displaying the human body).

Regarding the lost to follow-up and missing data, the most pejorative result already gathered about each score will be taken as a reference to complete missing data, for analysis by intention to treat.

Two blood samples will be carried out on each patient. The first will arrive in SSPI before infusion of ketamine. The following sample will be 4 hours after the end of the infusion or 6 hours after the start of the infusion in outpatient service. Sampling and dosing methodology is explained below.

In addition 24 samples will be collected without ketamine infusion (12 patients with bedsores and 12 without), to assess the effect of inflammation on kynurenine pathway.

Methodology of dosage

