In the follow-up phone calls and self-report at home will be considered follow-up. Missing data management has already been clarified above.

Assessment of treatment effectiveness

The effectiveness of the treatment will be judged on a reduction of more than 30% of the intensity of neuropathic pain evaluated at the moment on a numeric scale of 10 points between H0 (before infusion) and H4 (after the end of the infusion). This criterion will be assessed by one of the investigators of the study.

Assessment of the safety of the treatment

Infusion being made in recovery room, the usual follow-up of a patient in recovery room will be arranged: decision-making of the constants every 15 minutes including the oxygen saturation, blood pressure, heart rate, awareness of Glasgow score, the respiratory rate. Supervision of one hour after the end of the infusion will be implemented.

The release of recovery room will be one hour after the end of the infusion and with the usual criteria of output with Aldrete score.

Any adverse event during infusion will be reported to a doctor Anaesthesiologist resuscitator and will be declared.

If an adverse event occurs a period of hospitalization is equal to 5 times the half-life (3 hours about ketamine), more than 15 hours will be organized until total elimination of the product.

Sample size and statistical analysis

After data from a study underway by our team (study LIKE), the standard deviation of instant pain score is of 1.4 on the same model. We considered that an improvement of 30% in the score of the intensity is relief significant clinic. Based on these figures and assuming a risk $\alpha = 0.05$ and a risk $\beta = 0.90$, and using a one-sided Student's T test for a comparison of the 2 to 2 groups the minimum calculated sample size is 12 patients analyzed per group (for a total of 48 patients).

After checking the normality of distributions, comparison of continuous variables (Score, NPSI, pain, depression and biology Score) between the two groups will be analyzed with the Student's T test, variables with a no normal distribution will be analyzed with the non-parametric Mann-Whitney U test. p < 0.05 was considered statistically significant p-values. R and SPSS software will be used for the production of statistics.

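### The side-effect criterion is timed at H0, H4 and J1, and nothing brings the infusion and recovery observations, or a J4 or J7 question, into the comparison between arms

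*Combined protocol and SAP*

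**What the plan says.** The summary table lists ketamine side effects among the secondary criteria without times. The section Secondary evaluation criteria gives the only times: "Side effects of the drugs evaluated H0 and H4 of the end of the infusion then in J1".

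Information on benefits and risks of the product names the effects to expect: "The most common side effects are: drowsiness, euphoria, hallucinations, tinnitus, nightmares and disorientation, nystagmus", followed by arterial hypertension and tachycardia.

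Other sections bear on how such effects are observed and reported:

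- Assessment of the safety of the treatment sets checks every 15 minutes of oxygen saturation, blood pressure, heart rate, Glasgow score and respiratory rate. It adds one hour of supervision after the infusion and has any adverse event during the infusion reported to an anaesthetist and declared.
- Safety assessment and management of serious events makes the investigator responsible for reporting all adverse events. Risks incurred and constraints asks patients to tell the research doctor about any event during the study.
- Serious events have their own route: "Each observation will include a reporting of serious adverse events card", and the reporting duty continues "in the weeks after the discontinuation of treatment".
- Data collected on patients describes contact at J1, J4 and J7 by self-report or telephone for the NPSI and the painful area, with HADS at J7. It names no side-effect item.

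**The concern.** The criterion compares ketamine with placebo, so what counts is what is recorded in the same way in both arms and enters the analysis. At the stated times there is one assessment before any drug, one well after the infusion has stopped, and one the next day. Much is watched in between, but no section says that these observations count towards the criterion, and none says whether the H4 assessment asks about the whole interval since H0 or only about the patient's state at that moment.

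Two things are at stake. If H4 is a snapshot, transient effects during the infusion and the first hour of recovery drop out of the between-arm comparison, mostly from the ketamine arm. After J1, non-serious effects enter only if a patient or clinician raises them, although patients are contacted at J4 and J7 anyway. The trial has no oversight committee and plans a safety assessment at the interim analysis, so the side-effect table is the main comparative safety information it will produce.

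**Working it through.** The plan gives no figure to reproduce. The check is a timeline, followed by a comparison of sections.

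**Inputs**

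- Infusion: "it will be a single infusion of ketamine at a dose of 1 mg/kg, over a period of two hours" (Information on benefits and risks of the product).
- Second blood sample, which fixes the clock for H4: "4 hours after the end of the infusion or 6 hours after the start of the infusion" (Data collected on patients).
- H0 is before the infusion and H4 after its end (Assessment of treatment effectiveness).
- Checks every 15 minutes, and 1 h of supervision after the infusion (Assessment of the safety of the treatment).
- Half-life of about 3 h (same section, where the stay after an adverse event is set: "a period of hospitalization is equal to 5 times the half-life (3 hours about ketamine").

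**Timeline**

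- H4 from the start of infusion: 2 h + 4 h = 6 h, which agrees with the protocol.
- Infusion plus recovery: 2 h + 1 h = 3 h.
- Checks in that time, assuming the 15-minute interval holds throughout: 2 × 4 = 8 in the infusion and 1 × 4 = 4 in recovery, 12 in all. None is a time point of the criterion.
- From the end of supervision to H4: 6 h − 3 h = 3 h.

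**Drug level at H4, as an illustration**

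Assuming simple first-order decay after the infusion, the fraction of the end-of-infusion level left after t hours is 0.5^(t/3).

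| Time after end of infusion | Calculation | Fraction left |
|---|---|---|
| 0 h | 0.5^0 | 1.00 |
| 1 h | 0.5^(1/3) | 0.79 |
| 4 h (H4) | 0.5^(4/3) | 0.40 |

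H4 is thus 4/3 = 1.33 half-lives past the end. This shows that H4 lies well past the highest level. It says nothing directly about how often side effects occur.

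**Named effects against named checks**

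| Effect | Item in the 15-minute checks |
|---|---|
| Hypertension, tachycardia | Blood pressure, heart rate |
| Drowsiness, disorientation | Glasgow score, in part |
| Euphoria, hallucinations, tinnitus, nystagmus | None named |
| Nightmares | None; these arise later and depend on J1 or later contact |

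A marked psychodysleptic reaction is among the events that stop the infusion and are declared, so a severe reaction would be recorded as such. Milder psychic and sensory effects have no named item.

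**Two readings of the timing sentence**

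- *H0 before the infusion*, as the efficacy section defines it. There is a pre-drug baseline, and the next point comes 6 h after the start.
- *0 h and 4 h after the end of the infusion*. The wording allows this. The moment of highest level is then covered, but the 2 h of infusion are not, and no pre-drug baseline is left.

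**Analysis**

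Sample size and statistical analysis names tests for continuous variables only (scores, pain, depression, biology). No method is stated for comparing side-effect frequencies.

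**The case against.** The strongest reply is that the infusion and recovery period is closely observed. The patient is monitored every 15 minutes, any adverse event during the infusion is declared, Design of the study sends any potential adverse event to pharmacovigilance and the regulator, and the sponsor keeps detailed records of reported events. That stands. A reader might infer from the criterion's timing that side effects in these hours go unobserved, or that they rest on spontaneous reporting. The documents support neither: this is staff observation, and hypertension and tachycardia are measured systematically.

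A reader might also infer that the protocol's statement of minimal risk would be a trial conclusion drawn from the wrong window. It is not. Where it appears, it justifies the study in advance on the strength of prior experience.

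Three further points have force:

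- The list of data collected is not exhaustive, since its entries for the study period also omit the instantaneous pain score of the primary endpoint. The observation notebook is not among the documents. The lack of a page for non-serious effects therefore cannot be established; one can say only that none is named.
- H4 and J1 may be meant to cover the interval since the last assessment. The text allows this but does not say it.
- This is a single infusion, and the protocol's own rule puts elimination at about 5 × 3 h = 15 h, so J1 covers the first night. No section documents effects appearing at J4 or J7. The gap after J1 is the weaker half of the point.

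None of this supplies the link between what is observed and what the criterion compares.

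**Conclusion.** The point holds as a gap in structured capture and analysis, not in clinical observation. As written, none of the roughly 12 checks in the 3 h from start of infusion to the end of supervision feeds the side-effect criterion, four of the named acute effects have no item in those checks, and J4 and J7 carry no side-effect question.

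The direction of bias is conditional. If H0 is pre-infusion and H4 records only symptoms present at that moment, the ketamine-placebo difference in acute effects would probably be understated. That also assumes acute effects are greatest during or soon after the infusion, which the monitoring plan and the half-life suggest but the documents do not state. The size cannot be computed, because no side-effect rates are given; the 40% residual level only illustrates the timing and rests on simple first-order decay. If 0 h after the end was meant, the gap is smaller, but the infusion and the pre-drug baseline remain uncovered. If H4 asks about the whole interval, what remains is mainly reliance on recall.

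Severity: minor to moderate. It affects one secondary criterion and not the primary result.

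**What to change.** Reword the item under Secondary evaluation criteria as any side effect named in the benefit and risk section that occurs from the start of infusion to J7, compared by arm. Then:

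- Keep a pre-infusion entry as baseline, and say plainly what H0 and H4 mean for this criterion.
- Record the named effects on one checklist page during the infusion and recovery checks that already take place, and at the end of infusion.
- At H4 and J1, ask about the interval since the last assessment.
- Add one side-effect question at the existing J4 and J7 contacts.
- State in the analysis section that the number and proportion of patients with each effect will be reported by arm.

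To protect the blind, recovery-room staff other than the nurse who prepares the syringe should complete the infusion-period page. It should be kept from the pain assessor until the H4 pain score is recorded, because that score is the primary endpoint.

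The cost is one page and one question at each of two contacts. The downside is slightly more recording and a higher reported side-effect rate. The change concerns data collection and reporting only.

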resolution(30). There are few studies showing the effectiveness of ketamine administered by intra venous infusion in the treatment of refractory chronic pain medication (29). The recent literature reviews report the results in central neuropathic pain, especially in SCI patients (28,29).

50 to 80 percent of the SCI patients will develop at least an ulcer pressure over a lifetime. These pressure ulcers like all chronic wounds are factors of inflammation. This chronic inflammation in the zone under the injury, often insensitive, is a factor of awareness of the central nervous system. It is common to observe an exacerbation of chronic central neuropathic pain patients during inflammation. On the other hand, the clinical observations report often spectacular efficiency of ketamine on the neuropathic pain in those patients with bedsores.

Is this effect explained by a role on the kynurenine pathway in this population?

Would ketamine be more effective in this population?

Working hypothesis

The hypothesis that we raise, is : ketamine has an anti hyperalgesic action by anti inflammatory effects by interacting with the kynurenine pathway.

We test this hypothesis in a clinical study with ketamine in chronic pain patients with or without associated inflammation. Our choice of population is patients with spinal cord injury with central neuropathic pain. Part of this patient population frequently suffers from pressure sores which leads to chronic inflammation.

Trial purpose and goal:

Our clinical research aims to test the two following hypotheses

(1) The ketamine clinical effects on chronic neuropathic pain are more important when there is an associated inflammation.

(2) Its action is through interaction on the kynurenine pathway.

Methods

Population

The selected population is a population of SCI patients with central neuropathic pain at the level of injury or under injury, chronic (more than three months).

Patients are recruited through specialized consultation pain or bedscares consultation or through consultation and hospitalization in service of physical medicine and rehabilitation in hospital Raymond Poincare in Garches. This hospital is specialised in SCI management. The

Protocol will be proposed in a consultation of usual follow-up or hospitalization. The treatment will be initiated remotely, in a subsequent consultation scheduled apart of their follow-up.

Four groups of patients will be included:

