Group 1: SCI with central neuropathic pain with bedsore receiving ketamine infusion.

Group 2; SCI with central neuropathic pain with bedsore receiving placebo.

Group 3: SCI with central neuropathic pain without bedsore receiving a ketamine infusion.

Group 4: SCI with central neuropathic pain without bedsore receiving a placebo infusion.

Description of treatment (dosages, forms, packaging) and preparation of the product.

Ketamine: infusion IVSE of 1 mg/kg during 2 h in a 50 cc syringe Luer Lock BD Plastipack (100mg of Ketamine was 2 blisters 50mg / 5mL in a syringe of 50cc or a concentration of 2 mg/cc, speed = weight of the patient/4 mL/h).

A 50cc syringe Luer Lock Plastipack BD composed of Sodium chloride 0, 9% will be administered in the placebo group at the same rate in mL/h (weight of the patient/4 mL/h).

The 2 products are transparent, it will be impossible to differentiate the two products with the same packaging or a syringe with Luer Lock Plastipack BD 50 cc with a standard Extender for syringe Luer Lock.

Both products will be prepared by a nurse of SSPI, which won't participate in the study. The investigator responsible for the evaluation of the patient and the patient will remain blind to the administration of the product. Statistics will also be blind. Each syringe will be labeled only with patient number inclusion.

The infusion will be conducted in post operative monitoring room of the hospital Raymond Poincare in Garches, patients will be scoped and monitored for 1 h after the end of the infusion.

Design of the study

The study will be driving double blind, neither the patient nor the evaluator clinician will know product administered to the patient. The statistician who will analyze the data in the course of the study will be blind of the group in which the patient is located.

Randomization will be ensured by a randomization table created proactively using the R software between the two groups. The blind will be maintained through sealed envelopes. The post interventional monitoring room nurse will be the only one to know the contents of the envelope for the preparation of the drug. The investigator and the patient will remain blind to the treatment administered. The packaging is identical, the blind will be maintained throughout the study.

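### The non-inclusion list, read as written, rejects no-bedsore patients who are free of inflammatory disease, the opposite of what the inflamed versus non-inflamed comparison needs

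*Combined protocol and SAP*

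**What the plan says.** Under 'Patient selection, exclusion and data collected', the list headed 'No inclusion criteria' ends with this bullet: "For the group without sores, lack of ongoing inflammatory pathology noted by the interrogation (fever, sepsis, urinary tract infection".

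The only inclusion criterion that touches on bedsores is "SCI with central neuropathic pain with or without bed sores". It says nothing about inflammation.

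Elsewhere the plan makes bedsore its marker of inflammation and builds the trial on that contrast:

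- 'Description of the study population': "These pressure ulcers like all chronic wounds are factors of inflammation".
- 'Working hypothesis': "We test this hypothesis in a clinical study with ketamine in chronic pain patients with or without associated inflammation", followed by the reason for choosing this population: "Part of this patient population frequently suffers from pressure sores which leads to chronic inflammation".
- 'Trial purpose and goal', first hypothesis: "The ketamine clinical effects on chronic neuropathic pain are more important when there is an associated inflammation".
- 'Methods', the two comparison groups: "Group 3: SCI with central neuropathic pain without bedsore receiving a ketamine infusion" and "Group 4: SCI with central neuropathic pain without bedsore receiving a placebo infusion".
- 'Data collected on patients': samples from 12 patients with and 12 without bedsores, taken without ketamine, are meant to show what inflammation does to the kynurenine pathway.

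**The concern.** A non-inclusion criterion describes a patient who must not enter. Under that heading, a bullet naming the lack of inflammatory disease bars the non-inflamed patient, and for the no-bedsore group that is the patient the design requires.

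The first main objective in the study summary is to show that ketamine works better in patients with an inflammatory component. That needs a group with inflammation and a group without it. If the no-bedsore groups are filled with patients who have fever, sepsis or urinary infection, bedsore status no longer separates inflamed from non-inflamed patients. A similar ketamine effect in the two strata would then say nothing about the hypothesis. The comparison of samples taken without ketamine would have the same problem if those patients are screened by the same list.

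The wording also causes trouble if staff ignore it and follow the evident intent. Every correctly chosen no-bedsore patient would then meet a written non-inclusion criterion and could be recorded as an eligibility deviation.

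**Working it through.** **The plan's own figures.** 'Sample size and statistical analysis' gives 12 patients per group in four groups: 4 × 12 = 48. The 12 can be recovered if 30% is taken of a baseline of 6, the minimum pain score for entry. That baseline is an assumption, because the plan does not say which one it used.

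- Difference: 0.30 × 6 = 1.8 points; SD 1.4; one-sided α = 0.05; power 0.90.
- Normal approximation: n = 2 × (1.645 + 1.282)² × 1.4² / 1.8² ≈ 10.4, rounded up to 11.
- Exact one-sided t test: 12 per group.

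The point below does not depend on this calculation, and correcting the bullet leaves 12 and 48 unchanged.

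**Count of eligibility bullets.** There are 7 inclusion and 9 non-inclusion bullets, 7 + 9 = 16.

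- Non-inclusion bullets that state a reason to reject: 8 of 9. They are hypersensitivity, another trial, inability to consent, pregnancy or lactation, refusal to sign, cardiovascular disease, uncontrolled hypertension, and severe liver or kidney failure.
- Bullets that mention inflammation: 1 of 16, the one at issue.
- Laboratory thresholds for inflammation at entry: none. IL-1β, IL-6 and TNF-α are measured before infusion, but they are listed as outcomes.

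**The two readings side by side.**

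| | Read as a reason to reject (as placed) | Read as a requirement (evident intent) |
|---|---|---|
| No-bedsore patient, no inflammatory pathology | rejected | admitted |
| No-bedsore patient with fever, sepsis or urinary infection | admitted | rejected |
| Agrees with the first objective and first hypothesis | no | yes |
| Agrees with the with/without-inflammation design | no | yes |

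**Patients affected.** The bullet governs Groups 3 and 4: 2 × 12 = 24, and 24 / 48 = 50%.

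- As intended: 24 patients with bedsore against 24 with no inflammatory pathology noted at interview.
- As literally placed: 24 with bedsore + 24 without bedsore but with an inflammatory pathology = 48 of 48 inflamed, and 48 − 48 = 0 left for a non-inflamed comparison.

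The second count follows the plan's own terms: it calls pressure ulcers a source of inflammation and lists fever, sepsis and urinary infection as inflammatory pathology. Any figure for lost power would need the share of inflamed patients actually enrolled in Groups 3 and 4. The documents do not give it, so no such figure is offered.

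**The case against.** The strongest reply is that the intent is not in doubt. The title, the first objective, the working hypothesis, the group definitions and the sampling plan all point one way. The bullet opens by naming the group, so it can be read as describing what that group must satisfy, and its parenthesis lists conditions an interview would look for. The document shows many translation errors, and a single French hospital may well have screened from a French text that is not available here. The investigators who framed the hypothesis would be unlikely to fill their comparison group with febrile or septic patients. Pre-infusion cytokines would also reveal such patients afterwards.

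Much of this stands. A slip is the likeliest explanation, the practical risk at one specialised site is modest, and 48 of 48 is a limiting case. That count also treats an interview-noted fever or urinary infection as equivalent to the chronic inflammation of a pressure ulcer, which is a simplification. The point is best described as an internal inconsistency, not as a criticism of the design.

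It does not remove the point. An eligibility list is applied and audited as written, and a text outside the document cannot correct the one under review. The cytokines are outcomes and would detect a wrong enrolment only after the infusion. Clear intent elsewhere makes the correction easy; it does not make the line right.

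**Conclusion.** The concern holds. The bullet is wrong as written, in its wording or in its place, and contradicts the objective, hypothesis and group structure. It governs half of the planned sample (24 of 48), and no other eligibility criterion offsets it. Followed exactly, it removes the non-inflamed comparison group. Followed as intended, it protects that group but puts correctly enrolled patients in breach of the written list.

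The conclusion rests on reading the ninth bullet as the other eight are read, and on the plan's own use of bedsore as its marker of inflammation. That it is a slip is an inference, though a well-supported one. The correction should be made; the likely origin of the error argues against rating it any higher.

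**What to change.** Reconcile the bullet with 'Working hypothesis', the four group definitions and 'Data collected on patients'. Either of two edits does this:

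- Keep it in the non-inclusion list, but name the **presence** of an ongoing inflammatory pathology at interview as the reason not to include a no-bedsore patient, with the same three examples.
- Move the existing wording to the inclusion criteria, as a condition that applies to the no-bedsore group only.

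The cost is one reworded or relocated line. It needs no additional patients, visits or assays, and the sample size does not change.
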